3.4. Discontinuation Criteria

Subject participation may be discontinued in the following instances:

- Intercurrent illness that would, in the judgment of the investigator, affect assessments of clinical status to a significant degree.
- Unacceptable toxicity, or toxicity that, in the judgment of the investigator, compromises the ability to continue study-specific procedures or is considered to not be in the subject's best interest
- Relapse of primary disease
- Severity of cGVHD requiring therapy that is not allowed as concomitant therapy on study (for example JAK inhibitor/BTK inhibitor /mTOR inhibitors/ any cell depletion agent/ phototherapy)
- Subject request to discontinue for any reason
- Subject noncompliance
- Pregnancy during the study; refer to [Appendix 8](#)
- Discontinuation of the study at the request of Gilead, a regulatory agency or an Institutional Review Board or Independent Ethics Committee (IRB/IEC)

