6.5. Post-treatment Assessments

6.5.1. Unscheduled Visit

A subject should attend an unscheduled visit if requested by the Sponsor or the investigator. The assessments performed are at the investigator's discretion.

For subjects that initiate second line therapy during the study, every attempt should be made to collect the NCAA and LSS at an unscheduled visit and to keep the subject in the study and study related follow-up procedures should be continued.

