6.5.2. Early Study Drug Discontinuation (ESDD)

If the subject discontinues study drug prior to the end of study, the subject will be asked to return to the clinic within 72 hours of stopping study drug for the Early Study Drug Discontinuation Visit. The subject will be asked to continue attending the schedule study visits through Week 48. Subjects who ESDD will not be eligible for the OLE phase of the study.

At the ESDD visit, any evaluations showing abnormal results indicating that there is a possible or probable causal relationship with the study drug, should be repeated weekly (or as often as deemed prudent by the investigator) until the abnormality is resolved, returns to baseline, or is otherwise explained.

Evaluation listed in [Table 6-1](#) will be completed at the ESDD visit.

The following will be conducted at the ESDD: review of adverse events (AEs) and changes in concomitant medications, vital signs (including weight), complete physical exam, primary malignancy assessment (if applicable), blood for hematology, chemistry, metabolic panel, selected biomarkers and urine for: pregnancy test (if applicable), and urinalysis. The NCAA and LSS will be assessed.

PFTs will be required at ESDD: spirometry with bronchodilator and diffusing capacity of the lungs for carbon monoxide (DLCO).

6.6. 30 Day Follow-Up Visit

Subjects who complete through Week 48 visit and who do not wish to participate in the OLE phase of the study will return to the clinic 30 days after the completion of study drug for the 30-Day follow-up visit. Subjects who complete the OLE will return to the clinic 30 days after the completion of study drug for the 30-Day follow-up visit

Subjects who permanently discontinue study drug and refuse to continue in the study will be asked to return to the clinic 30 days after the completion of the ESDD visit for the 30-Day follow-up visit.

For the purpose of scheduling a 30-Day follow-up visit, a ± 5 days window may be used. [Table 6-1](#) lists all procedures to be completed at the 30-Day Follow-up visit.

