6. EFFICACY ANALYSES

6.1. Definition of the Primary Efficacy Endpoint

The primary endpoint is BORR by 24 weeks, defined as the proportion of subjects who achieve a complete or partial overall response (CR or PR) as assessed by the NCAA (Appendix 3) within 24 weeks, in the setting of add-on therapy to systemic corticosteroids as part of first-line therapy for cGVHD.

At each assessment time point, organ-specific responses will be determined according to Appendix 2. An overall time point response across all involved organs will then be determined according to Table 3. The best overall response across all time points up to 24 weeks will be used to calculate BORR by 24 weeks.

Table 3. Criteria for time point response determination

Response Category	Response Criteria
Complete response (CR)	Resolution of all cGVHD manifestations in each organ or site as described in the NCAA organ response determination table
Partial response (PR)	Improvement of at least 1 organ or site, without progression in any other organ or site as described in the NCAA organ response determination table.
Stable disease (SD)	Neither sufficient improvement to qualify for a PR nor sufficient decline to qualify for a PD
Progressive disease (PD)* * A flare is defined as acute worsening of signs and symptoms in any organ or site that occurs at least 4 weeks after PR/CR is achieved, which lasts ≤ 4 weeks.	
 • Worsening of signs and symptoms in any organ or site as described in the NCAA organ response determination table, taking the baseline as reference. OR • Increase in systemic corticosteroid dose to ≥ baseline dose (1 mg/kg/day) OR • Initiation of systemic immunosuppressive therapy other than systemic corticosteroids

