6.4. Secondary Efficacy Endpoints

6.4.1. Definition of Secondary Efficacy Endpoints

The key secondary endpoints are:

- Change from baseline in the skin domain of the LSS at 24 weeks
- Change from baseline in the mouth domain of the LSS at 24 weeks
- Change from baseline in the eyes domain of the LSS at 24 weeks
- Change from baseline in the total score of the LSS at 24 Weeks

Other secondary endpoints include:

- Duration of response, defined as the time from the documentation of BORR to the documentation of PD as defined in [Table 3](#). Note that a flare does *not* constitute an end to response. A sensitivity analysis for DOR could consider a flare does constitute an end to response.
- Proportion of subjects who ever achieve at least 50% reduction in systemic corticosteroid dose relative to baseline, where % reduction is calculated as (systemic corticosteroid dose at 24 weeks – baseline systemic corticosteroid dose) / baseline systemic corticosteroid dose.
- Proportion of subjects who initiate second-line therapy for cGVHD, defined as receiving any therapy besides systemic corticosteroids or study drug for the treatment of cGVHD. Inhaled and topical steroids are not considered second-line therapy.
- Failure-free survival (FFS), defined as the time from randomization to the earliest of first documentation of systemic therapy change, non-relapse mortality, or recurrent malignancy

- Safety and tolerability of ENTO

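### The rescue criterion for progressive disease does not clearly cover phototherapy, so duration of response could run through rescue and a response after rescue could enter BORR

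*SAP*

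**What the plan says.** SAP 6.1, Table 3, gives three routes to PD at a time point:

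- "Worsening of signs and symptoms in any organ or site as described in the NCAA organ response determination table, taking the baseline as reference";
- a rise in systemic corticosteroid dose to at least the baseline dose;
- "Initiation of systemic immunosuppressive therapy other than systemic corticosteroids".

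Protocol Table 8-1 words the third route identically. Best overall response is the best result over all time points up to 24 weeks. DOR runs from response to PD as defined in Table 3.

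Protocol 3.4 names the therapies not allowed for severe cGVHD: "JAK inhibitor/BTK inhibitor /mTOR inhibitors/ any cell depletion agent/ phototherapy". Phototherapy is also a row of Table 5-2 (prohibited agents), and exclusion criterion 2d bars earlier post-transplant use except for acute GVHD.

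The second-line endpoint in SAP 6.4.1 has a wider net, "defined as receiving any therapy besides systemic corticosteroids or study drug for the treatment of cGVHD", with inhaled and topical steroids exempt.

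Stopping is permissive: "Subject participation may be discontinued in the following instances". For subjects who start second-line therapy, "every attempt should be made to collect the NCAA and LSS at an unscheduled visit and to keep the subject in the study" (protocol 6.5.1). For those who stop study drug, "The subject will be asked to continue attending the schedule study visits through Week 48" (protocol 6.5.2).

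**The concern.** The protocol foresees phototherapy as something a subject with severe cGVHD may come to need, and it groups phototherapy with agents whose start would plainly be PD. The PD criterion uses a narrower description, and phototherapy may or may not fit it. One event is therefore second-line therapy in one endpoint and undetermined in the primary endpoint and in DOR. Two programmers could code it differently and both could defend the choice.

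DOR is the more direct exposure, because PD is the only event that ends it. BORR is exposed too, since NCAA assessments continue after rescue and no rule removes them. If rescue is commoner in the arm with more failures, the effect on BORR is to narrow the difference.

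**Working it through.** **1. Follow one subject through the rules.** Take a subject with no organ worse than baseline and no steroid increase to the baseline dose, who starts phototherapy for cGVHD at Week 12.

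| Rule | Result |
|---|---|
| SAP 6.4.1, second-line therapy | Event |
| Table 3, organ worsening | Not met |
| Table 3, steroid increase | Not met |
| Table 3, new systemic immunosuppression | Not determined: phototherapy is undefined |
| Protocol 6.5.1 and 6.5.2 | Follow-up and NCAA continue if the subject stays |
| Table 3, PR at Week 16-24 | Met if one organ improves and none progresses |

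If the undetermined row is read as not met, a prior responder has no end date for DOR and a prior non-responder can become a BORR responder. The partial-response wording in the protocol synopsis does not settle it, because it too refers only to additional systemic therapy. If phototherapy were treated as local, protocol 5.4 would point to judging the response on the NCAA alone.

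**2. Reproduce the plan's own figure.** Inputs from SAP 1.3: 50% versus 80%, 40 per group, two-sided 0.05, Fisher's exact test. Exact enumeration gives power 0.749, against the stated 75%. With 20% dropout, 40 / (1 - 0.20) = 50 per group, 100 in total. The sample-size arithmetic is sound and this point does not affect it.

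**3. Size the effect on BORR.** Let f be the share of non-responders who start phototherapy before Week 24, and q the share of those who then meet CR or PR and are counted. Both are assumptions; the documents give neither. In an arm with response rate p:

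counted rate = p + (1 - p) x f x q

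With p = 0.50 and 0.80 and the same f and q in both arms:

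difference = (0.80 + 0.20fq) - (0.50 + 0.50fq) = 0.30 x (1 - fq)

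| f | q | fq | Placebo | ENTO | Difference (points) | Power, 40 per group |
|---|---|---|---|---|---|---|
| 0 | - | 0 | 50.0% | 80.0% | 30.0 | 0.749 |
| 5% | 50% | 0.025 | 51.25% | 80.5% | 29.25 | 0.730 |
| 10% | 50% | 0.05 | 52.5% | 81.0% | 28.5 | 0.711 |
| 20% | 50% | 0.10 | 55.0% | 82.0% | 27.0 | 0.673 |
| 20% | 70% | 0.14 | 57.0% | 82.8% | 25.8 | between 0.673 and 0.594 |

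The lower power bound in the last row is the value at fq = 0.20 (f = 20%, q = 100%).

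**4. Unequal use.** Suppose both true rates are 50%, with 50 per group, and only one arm has counted post-phototherapy responses. With f = 10% and q = 50% that arm's rate is 0.50 + 0.50 x 0.05 = 0.525, and Fisher's test rejects with probability 0.041 instead of 0.035. With f = 20% and q = 50% the rate is 0.55 and the probability is 0.058.

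**5. Would coding PD on the start date be enough?** For DOR, yes. For BORR, no. Table 3 classifies single time points and BORR takes the best of them, so a CR or PR after the PD date would still be eligible unless the plan excludes it.

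**The case against.** A reader might infer that phototherapy is definitely not PD and that any later improvement counts as a study-drug response. The documents do not support that. They never say that phototherapy is non-systemic, and they list it beside agents that clearly are. Many subjects who need it may already be PD by organ worsening or a steroid increase. A later improvement must meet the NCAA thresholds for CR or PR, without progression elsewhere, by Week 24, and it changes BORR only in a subject with no earlier response. All of this stands, so the finding is one of ambiguity affecting a subset.

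Other arguments on that side:

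- **A narrower PD trigger may be deliberate.** The second-line definition could take in eye drops, which protocol 5.4 judges on the NCAA. This is a fair reason not to import that definition whole. It does not explain leaving open a therapy that the protocol prohibits.
- **Prohibition and possible withdrawal limit use.** True, but withdrawal is optional and the protocol asks for continued follow-up.
- **BORR dilution is not specific to phototherapy.** Correct. A response after a JAK inhibitor is not excluded either, which is why the fix needs a sentence on post-rescue assessments.
- **The bias is towards the null.** That is so with equal use in both arms at the planned rates. Step 4 shows it is not guaranteed when use differs.
- **SAP 3.5 drops formal comparisons after early termination.** True, and it lowers the stakes. SAP 6.3 still reports response rates, their difference and confidence intervals, 6.4.2 still reports DOR, and under SAP 2.2 DOR was among the data for DMC review if the futility threshold was crossed.

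**Conclusion.** The point holds as an ambiguity in endpoint coding. For a subject without organ worsening against baseline or a qualifying steroid increase, starting phototherapy for cGVHD is not clearly PD. The consequence for DOR is direct but cannot be sized from the documents. For BORR, the 30-point difference would fall to about 29-26 points if 5-20% of non-responders start phototherapy and 50-70% of them then respond. That range assumes equal use in both arms, that every such response is counted, and that the planning rates of 50% and 80% exclude such responses. The frequencies are illustrative. This is a minor point, worth correcting because the response rates and DOR are still to be reported.

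**What to change.** In SAP Table 3 and protocol Table 8-1, reword the third PD criterion so that starting, for cGVHD, any therapy listed as not allowed in protocol 3.4 or Table 5-2 (naming phototherapy), or any other new systemic immunosuppressive therapy, is PD on its start date. Add one sentence to SAP 6.1: assessments after that date do not contribute to best overall response. The first change settles DOR; BORR needs both. Permitted local treatment stays judged on the NCAA.

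This is endpoint coding only and changes no care. The cost is a few more PD events, possibly in both arms, and a check that the eCRF captures phototherapy start dates. The concomitant-medication footnote to the schedule of assessments does not name phototherapy. Being named there would not settle the matter either: the footnote names PPI, and the SAP revision log says PPI use was not recorded in the eCRF.

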6.2. Statistical Hypothesis for the Primary Efficacy Endpoint

The primary analysis will test the null hypothesis (H_0) that there is no difference in BORR between ENTO and placebo versus the alternative hypothesis (H_1) that there is a difference. Formally,

$$H_0: R_1 = R_0 \text{ vs. } H_1: R_1 \neq R_0,$$

where R_1 and R_0 are the BORR rate for ENTO and placebo treatment groups, respectively.

6.3. Analysis of the Primary Efficacy Endpoint

The primary analysis for BORR will be performed in the ITT Analysis Set, which includes all subjects who were randomized. Response rate will be summarized by count and percent of subjects with each ordinal response (CR, PR, CR or PR, SD and PD). A stratified Cochran-Mantel-Haenszel (CMH) Chi-square test will be performed to compare BORR (CR + PR) between ENTO and placebo-to-match (PTM) by 24 weeks. The difference in response rates between treatment groups and the corresponding 95% CIs will be presented.

If the entire NIH questionnaire is missing, then the organ and subject level statuses are missing. Missing individual NIH domain scores, for example, skin score, will lead to missing status for skin domain. In such a case, the subject level status will be based on the remaining available domain statuses. This is equivalent to imputing the missing domain status as ND or NA.

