3.6. Missing Data and Outliers

3.6.1. Missing Data

Missing data can have an impact upon the interpretation of the trial results. In general, values for missing data will not be imputed unless methods for handling missing data are specified. The handling of missing or incomplete dates is described in Section 7.1.5.2 for AE onset, in Section 6.3 for efficacy, in Section 7.4 for prior and concomitant medications, and in Section 7.1.5.2 for missing last dose date.

Values for missing safety laboratory data will not be imputed; however, a missing Baseline/Day 1 result will be replaced with a screening result, if available. If no pre-treatment safety laboratory value is available, the Baseline/Day 1 value will be assumed to be normal (ie, no grade) in the summary of graded laboratory abnormalities. Values for missing vital signs data will not be

imputed; however, a missing Baseline/Day 1 result will be replaced with a screening result, if available.

- If safety laboratory results for a subject are missing for any reason at a time point, the subject will be excluded from the calculation of summary statistics for that time point. If the subject is missing a pre-dose value, then the subject will be excluded from the calculation of summary statistics for the pre-dose value and the change from pre-dose values.

SAS code to calculate the LSS score and handle missing data are provided in [Appendix 6](#).

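### SAP 6.3 leaves undefined how BORR counts a randomised subject with no usable post-baseline NCAA, and lets a visit with an unscored involved organ be called CR

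*SAP*

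**What the plan says.** Four statements in the SAP have to be read together.

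- **Population (6.3):** "The primary analysis for BORR will be performed in the ITT Analysis Set, which includes all subjects who were randomized".
- **Whole questionnaire missing (6.3):** "If the entire NIH questionnaire is missing, then the organ and subject level statuses are missing". The revision log dates this text to 24 APR 2018, in the revision that records the discontinuation of the study.
- **Default (3.6.1):** "In general, values for missing data will not be imputed unless methods for handling missing data are specified". For efficacy, 3.6.1 refers the reader to 6.3.
- **Single domain missing (6.3):** the subject-level status is taken from the remaining domains, and the SAP adds: "This is equivalent to imputing the missing domain status as ND or NA".

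The BORR table in 6.3 has rows for CR, PR, CR or PR, SD and PD, with none for missing or not evaluable. The endpoint in 6.1 is "defined as the proportion of subjects who achieve a complete or partial overall response (CR or PR) as assessed by the NCAA", taken as the best response over all time points up to 24 weeks. Neither document contains a rule that counts a subject without a response assessment as a non-responder.

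**The concern.** The rate, its confidence interval and any CMH test all need a denominator, and the text allows two. If missing status is carried through and the default in 3.6.1 applies, a subject with no usable post-baseline NCAA has no value to tabulate. Most software would drop that subject, and the analysis would no longer cover everyone randomised. If the endpoint definition governs, the same subject has not achieved CR or PR and counts as a non-responder. Two analysts following the SAP could report different BORR results from the same data.

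Subjects lost before any usable assessment may have left because of toxicity or worsening disease, and such loss can differ by arm. Excluding them raises the observed rate in the arm that loses more of them.

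The domain rule raises a narrower question. CR in SAP Table 3 requires resolution in each organ or site. An organ involved at baseline but not scored at a visit is treated as not done or not applicable, so it cannot prevent a CR at that visit.

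**Working it through.** **Inputs from SAP 1.3.** 40 analysed per arm, 50 enrolled per arm, 20% dropout, placebo response 50%, a 30% improvement, Fisher's exact test at two-sided 0.05, stated power 75%. The share of subjects with no usable post-baseline NCAA, written *m*, is not given, so every *m* below is an assumption.

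**1. The plan's own figure.** Power is the sum over (x1, x0) of Bin(x1; 40, 0.80) × Bin(x0; 40, 0.50) × I(Fisher p < 0.05) = 0.749. This reproduces 75%, with the 30% read as percentage points. Read as a relative increase (50% to 65%), power would be 0.213. Enrolment is 40/(1 − 0.20) = 50 per arm, or 100 in total, which also agrees.

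**2. Power under the two denominators.** Assume 80% and 50% respond among assessed subjects, with the same *m* in each arm. Exclusion analyses about 50(1 − m) per arm at 80% and 50%. The non-responder rule analyses 50 per arm at 0.80(1 − m) and 0.50(1 − m).

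| m | Rates, all 50 per arm | Power, non-responder rule | Power, exclusion |
|---|---|---|---|
| 2% | 78.4% v 49% | 0.830 | 0.842 |
| 5% | 76% v 47.5% | 0.796 | 0.831 |
| 10% | 72% v 45% | 0.739 | 0.815 |
| 15% | 68% v 42.5% | 0.683 | 0.783 |
| 20% | 64% v 40% | 0.624 | 0.749 |

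The last row takes all of the planned dropout as having no usable response. The stated 75% matches the exclusion column there. In one data set at those rates, 32/40 v 20/40 gives Fisher p = 0.009, while 32/50 v 20/50 gives p = 0.027.

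**3. Bias when loss differs by arm.** Suppose 25 of 50 truly respond in each arm and every missing subject is a non-responder. Exclusion then gives 25/(50 − missing).

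| Missing, ENTO / placebo | Rates after exclusion | Spurious difference |
|---|---|---|
| 2 / 0 | 52.1% v 50.0% | 2.1 points |
| 5 / 0 | 55.6% v 50.0% | 5.6 points |
| 10 / 0 | 62.5% v 50.0% | 12.5 points |
| 10 / 5 | 62.5% v 55.6% | 6.9 points |
| 10 / 10 | 62.5% v 62.5% | 0 |

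Under the same assumptions, the simulated type I error of a single-stratum CMH test after exclusion is:

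- no loss: 0.056
- 10% loss in each arm: 0.050
- 10% v 0%: 0.084
- 20% v 10%: 0.098
- 20% v 0%: 0.220

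Balanced loss does no harm to the comparison. Unequal loss does.

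**4. The domain rule.** Take a subject with two organs involved at baseline. At one visit the first has resolved and the second is not scored. Under 6.3 the status rests on the first organ alone, so the visit can be CR. If the second organ were still involved but not worse, the correct status would be PR. BORR counts CR and PR alike, so CR+PR is unchanged. It would change only if the unscored organ had progressed, because that would block PR.

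**The case against.** A reader might infer that the SAP removes randomised subjects from the CMH test, so that the primary analysis is not ITT. The documents do not support that.

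- No section says that subjects with missing status leave the test. SAP 3.1.1 makes ITT the primary set for efficacy. Under 6.1, a subject with no documented CR or PR has not achieved one.
- The Appendix 5 code for the final two-by-two table takes non-responses as full arm size minus responders. It was written for predictive probability and does not specify the CMH analysis, but it points the same way.
- The missing-status sentence reads most naturally per visit. Table 6-1 schedules the NCAA at weeks 4, 8, 12, 16, 20 and 24, and one missed visit leaves the others to supply the best response.
- Protocol 6.5.2 asks for an NCAA within 72 hours of stopping drug and for continued visits through week 48. Protocol 6.5.1 and Table 6-1 ask for one when second-line therapy starts. SAP Table 3 also assigns PD from a steroid increase or new systemic immunosuppression without any organ score. The affected group should therefore be small.

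These points stand, and they limit the finding to an undefined outcome. Two further inferences also fail. The sample-size basis of 40 out of 50 fits exclusion but does not prove it, and the 20% dropout is not a rate of having no NCAA. The entry for non-responder imputation in the protocol glossary proves nothing, since LOCF is listed there and is equally unused.

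SAP 3.5 says no formal comparisons will be done after early termination, while 6.3 keeps the CMH test. That lowers the stakes for the p-value, but the percentages and the interval still need a denominator. SAP 6.6 is redacted and may hold further text on missing data.

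On domains, protocol 6.4 allows an organ assessment to be deferred while the others are scored, so using the available domains has a basis. A reader might also infer that the rule inflates BORR. Step 4 shows that it usually does not.

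**Conclusion.** The concern holds as a gap in definition. SAP 6.3 and 3.6.1 together leave a randomised subject with no usable post-baseline NCAA by week 24 without a BORR outcome. The default handling of a missing value would contradict the stated population, while SAP 6.1 and Appendix 5 point to the full arm.

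The size depends on figures that the documents do not give. Under the assumptions in step 3, a one-arm loss of 2 to 10 out of 50 creates a spurious difference of 2.1 to 12.5 points, and equal loss creates none. These figures use the planned arm sizes and treat every missing subject as a true non-responder.

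The domain rule is explicit, and it can overstate the CR count. Its effect on CR+PR is limited to visits where an unscored organ had in fact progressed.

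**What to change.** In SAP 6.3:

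1. State that every randomised subject without a documented CR or PR by week 24, including those with no usable post-baseline NCAA, counts as a non-responder and stays in the denominator of the rate, the confidence interval and any CMH test.
2. Add a not-evaluable row to the response table, by arm, so that the extent and balance of loss can be seen.
3. State that a visit at which a domain involved at baseline is missing cannot be CR, and is at most PR. This corrects the CR count. It does not address unseen progression in the unscored organ.
4. Give an observed-case analysis as a sensitivity analysis.

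The cost is a few sentences and one table row. BORR percentages become slightly lower. Power falls below the exclusion figure by an amount that grows with the share not assessed: 0.830 against 0.842 at 2%, and 0.624 against 0.749 if all of the planned 20% dropout lacked a usable response.

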6.4.2. Analysis Methods for Secondary Efficacy Endpoints

The key secondary endpoints will be analyzed using a two sample z-test at week 24.

Other secondary endpoints will be analyzed as follows:

DOR and FFS will be analyzed using the Kaplan-Meier (KM) method and stratified logrank test. Kaplan-Meier summary statistics (median, 95% CI for median, and 25th, 75th percentiles) and number and percentage of events will be presented by treatment group. A stratified Cox proportional hazards model will be used to estimate the hazard ratio and corresponding 95% CI. A KM survival plot will also be provided. Data for subjects who do not experience an event will be censored at the date of last visit. DOR will be analyzed only on subjects who responded.

Proportion of subjects with at least 50% reduction in systemic corticosteroid dose relative to baseline and proportion of subjects who initiated a second-line therapy for cGVHD will be analyzed similarly to the primary endpoint.

Line plot of change from baseline in each domain and total of LSS will be done.

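### The missing-questionnaire rule in SAP 6.3 conflicts with the treatment-based PD criteria in SAP Table 3, so a documented progression can be delayed or lost in DOR

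*SAP*

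**What the plan says.** SAP 6.1 determines an overall response at each assessment time point from Table 3. The PD row of that table joins three criteria by OR:

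- Organ worsening: "Worsening of signs and symptoms in any organ or site as described in the NCAA organ response determination table, taking the baseline as reference". This needs the NCAA.
- A rise in systemic corticosteroid dose to the baseline dose or above. This is a medication-record fact.
- "Initiation of systemic immunosuppressive therapy other than systemic corticosteroids". This is also a medication-record fact.

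SAP 6.3 then gives the missing-data rule: "If the entire NIH questionnaire is missing, then the organ and subject level statuses are missing". For a partly completed form it continues: "In such a case, the subject level status will be based on the remaining available domain statuses".

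SAP 6.4.1 defines DOR as "the time from the documentation of BORR to the documentation of PD", with PD as in Table 3. SAP 6.4.2 analyses DOR in responders only, by Kaplan-Meier, stratified logrank and stratified Cox, and adds: "Data for subjects who do not experience an event will be censored at the date of last visit".

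Steroid dose and other immunosuppressives are collected as concomitant medication at every visit (Protocol Table 6-1, footnote r). Dose changes and start and end dates are required source data (Protocol 9.1.5).

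**The concern.** Read as written, SAP 6.3 turns a visit with a known treatment failure into a missing status because a form was not completed. Table 3 calls the same visit PD. The two rules give different answers for the same data, and no text ranks them or dates a treatment-based PD. Two competent programmers could therefore produce different DOR results.

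Under the literal reading, the events at risk are those of responders who have just needed more treatment. If such a subject has no further NCAA, the event becomes a censoring at last visit. That censoring is informative, and it lengthens the estimated DOR. The best-response table, which reports CR, PR, SD and PD, could also show too few subjects with PD.

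**Working it through.** **The plan's own figure.** The plan gives no event count or power for DOR. Its only power figure concerns BORR: 75% with 40 per group, Fisher's exact test, 80% against 50% (reading the 30% improvement as absolute). Exact enumeration gives 74.9%. This point does not touch that figure.

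**Where the rules diverge.** Take a visit with no NCAA but a recorded steroid increase or new systemic immunosuppressant:

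| Source | Result for that visit |
|---|---|
| SAP Table 3, second or third PD criterion | PD |
| SAP 6.3, read literally | Missing |
| SAP 6.4.1, if DOR is taken straight from Table 3 | DOR event |
| SAP 6.4.1 and 6.4.2, if DOR is built on the 6.3 status | No event at that visit; censored at last visit if none follows |

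**Delay or loss.** NCAA visits are 4 weeks apart from Week 4 to Week 24 and 6 weeks apart to Week 48 (Protocol Table 6-1). If the new therapy is recognised, or the dose is still at or above baseline, at the next NCAA, PD is about one visit late. It is lost if there is no later NCAA or the dose has fallen again.

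- *Steroid criterion.* Protocol 5.4 has prednisone raised by two levels, given daily for 2 to 4 weeks, when cGVHD recurs during the taper. In Table 5-1, two levels above 0.5 mg/kg daily is 1.0 mg/kg daily, which meets the Table 3 criterion. One missed NCAA leaves a gap of 2 × 4 = 8 to 2 × 6 = 12 weeks, so such an increase can start and end inside it. The protocol does not call for an NCAA at a steroid increase.
- *New-therapy criterion.* The protocol asks for an NCAA when second-line therapy starts (Table 6-1 footnote g; 6.4), and 6.5.1 says "every attempt should be made to collect the NCAA and LSS at an unscheduled visit". Protocol 6.5.2 adds an NCAA at the early-discontinuation visit. The gap is smaller here. It is not closed, because Protocol 3.4 lists cGVHD needing disallowed therapy among the reasons for ending participation.

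**Endpoints touched.**

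- BORR: neither missing nor PD is CR or PR, the denominator is all randomized subjects, and SAP 6.1 takes the best response over all time points up to 24 weeks. The label makes no difference.
- FFS: defined from systemic therapy change, non-relapse mortality and recurrent malignancy. It does not use the 6.3 status.
- PD count: any evaluable NCAA up to Week 24 gives CR, PR or SD, which outrank PD, or gives PD itself. Only subjects with no evaluable post-baseline NCAA in that period can be misclassified.
- DOR: affected only if built on the 6.3 status.

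**Illustrative size for DOR (all inputs assumed).** Suppose 40% of responders have PD within 24 weeks of response, with a constant hazard.

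- h = −ln(0.6)/24 = 0.02128 per week; median = ln 2/h = 32.6 weeks.
- If a fraction f of events is lost, the hazard becomes h(1 − f), the median 32.6/(1 − f), and the 24-week PD proportion 1 − 0.6^(1 − f).

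| f | Apparent median DOR (weeks) | Apparent 24-week PD |
|---|---|---|
| 0 | 32.6 | 40.0% |
| 0.10 | 36.2 | 36.9% |
| 1/6 | 39.1 | 34.7% |
| 0.25 | 43.4 | 31.8% |

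To see what might produce f, let q be the share of PD events that rest on treatment criteria alone and m the share of those never recovered by an NCAA, so that f = q × m. For q from 0.25 to 0.75 and m from 0.1 to 0.4, f runs from 0.025 to 0.30 and the median is multiplied by 1/(1 − f), that is 1.03 to 1.43.

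Unequal loss would also distort the hazard ratio. With a true ratio of 1, q = 0.5, and m of 0.1 in one arm and 0.4 in the other, the apparent ratio is 0.95/0.80 = 1.19 or 0.80/0.95 = 0.84.

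**The case against.** The strongest reply is that SAP 6.4.1 ties DOR directly to PD as defined in Table 3, and does not mention the 6.3 status. On that reading, a steroid- or therapy-based PD is a DOR event by definition. SAP 6.3 also sits under the primary endpoint and builds its status from organ domains, so its subject-level status may mean only the organ roll-up. Both readings are tenable. Neither is stated: 6.3 names the subject level separately from the organ level, and Table 3 is applied at assessment time points.

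A reader might go further and infer that treatment failures do drop out of DOR, and that DOR is overstated in both arms, more so where rescue and dropout are commoner. The documents do not support that. The loss depends on how DOR is programmed, later visits will often recover the event, and nothing indicates that missing forms will differ by arm. Nor does Protocol 6.5.1 show that the sponsor expects NCAA forms to be missed at second-line start. Together with Table 6-1, 6.4 and 6.5.2, it asks for them.

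The context also limits the weight. The study was stopped for lack of efficacy (SAP 2.3), SAP 3.5 says there will be no formal comparisons, and DOR is a non-key secondary endpoint in responders. Even so, SAP 6.4.2 still plans the Kaplan-Meier, logrank and Cox analyses of DOR. SAP 11 records the sentence on the missing questionnaire as an addition meant to clarify missing-data handling, which is a reason to make it unambiguous.

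**Conclusion.** The conflict between SAP 6.3 and Table 3 is real and unresolved in the documents. Its effect on DOR is conditional: if DOR is programmed from the 6.3 visit status, a documented treatment-based PD is delayed to the next NCAA, or is lost and informatively censored when no later NCAA exists or the dose has fallen again. The PD count is exposed only through subjects without an evaluable post-baseline NCAA up to Week 24. BORR and FFS stand.

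The size cannot be computed from the documents. The shift from 32.6 weeks to between 36.2 and 43.4 weeks rests on an assumed 40% PD at 24 weeks, a constant hazard, and permanent loss of 10% to 25% of events. The upper value is near the limit of what blinded follow-up could show: the first post-baseline NCAA is at Week 4, leaving at most 48 − 4 = 44 weeks. The point merits correction because the remedy is specific and costs little, not because a large bias has been shown.

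**What to change.** In SAP 6.3, limit the missing-questionnaire rule to the organ criterion, the first PD bullet of Table 3. Then state that the other two PD criteria:

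- are derived from the steroid-dose and concomitant-medication records;
- are dated at the start of the dose increase or of the new therapy;
- count as PD, both as the DOR event and in the PD count of the best-response table, whether or not an NCAA was done.

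The cost is SAP wording and one derivation from data already collected.
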